Sampling for pharmacokinetic assessments ^h			X	X	X	X	
Sampling for pharmacodynamic assessments ^{h,i}		X	X	X	X	X	X
Hot Flashes Severity and Frequency ^j		X	X	X	X	X	X
Hot Flash Related Daily Interference Scale ^k			X	X	X	X	X
Leeds Sleep Evaluation Questionnaire ^l			X	X	X	X	X
Greene Climacteric Scale ^l			X	X	X	X	X
Sheehan Disability Scale ^l			X	X	X	X	X
Clinical laboratory tests and urinalysis ^m		X	X	X	X	X	X
Bone density markers ⁿ			X			X	
Vital signs ^o		X	X	X	X	X	X
ECG ^p		X	X	X		X	X
Randomization			X				
ePRO training		X					
Dispensing of study drug ^q			X	X	X		
Intake of study drug ^r			X	X	X	X	
Compliance ^s				X	X	X	
Concomitant therapies ^t		X	X	X	X	X	X
Adverse events ^t		X	X	X	X	X	X

Footnotes on the next page.

- a. All visits need to be planned in the morning, fasted (for unbiased glucose, insulin, and C-peptide determination). Visit 2 should be planned to allow for first intake of study drugs at the clinical site, between 7:00 and 10:00 AM. For each subject, all visits during the treatment period subsequent to Visit 2 should be planned at the same time of the day, in the morning. A deviation of ± 1 day is allowed on the visits during the treatment period subsequent to the first study drug intake (Visits 3-5).
- b. Screening is to be performed within 4 weeks prior to the first intake of study drug, with a minimum of 7 days to allow for baseline data collection of Hot Flash Score and Hot Flash Frequency.
- c. Two to 3 weeks after the last intake of study drug.
- d. No study-related assessments are to be carried out before signing of the informed consent form.
- e. Includes height, weight, and waist circumference (height at screening only).
- f. Includes HBsAg, and anti-HCV and HIV antibodies.
- g. For practical reasons, the timing of DEXA may vary from the actual time of the visit, depending on DEXA availability (DEXA appointment). The Visit 2 DEXA can be performed prior to Visit 2 during the screening period, as well as at Visit 2 but must be performed before randomization. The Visit 5 DEXA can be performed ± 4 days from the actual time of Visit 5. It is however to be performed before the last dose of the study drug; in case the DEXA appointment related to Visit 5 is scheduled later in time than Visit 5, study drug intake must be continued until DEXA has been performed.
- h. Predose at Visits 2, 3, and 4; predose and 3 hours postdose at Visit 5.

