Following multiple dose administration for 21 days in healthy females, it could be concluded that steady-state in ESN364 plasma concentrations was reached quickly, by Day 2, so after the first administration of study drug. The bioavailability of ESN364 increased dose proportionally between 20 and 60 mg q.d. but was above the dose proportionality for the highest 180 mg q.d. compared to 60 mg q.d., as measured by peak and plasma exposure, and this independently from PK sampling day (Day 1 and Day 21). No significant dose and day effects were observed on t_{max} with median t_{max} of 3.00 to 4.00 hours. Plasma ESN364 exposure was higher at steady-state (Day 21) compared to Day 1. From descriptive data, the apparent elimination half-life seems to be comparable between the studied dose groups as well between single dosing and steady-state (mean half-life ranged between 4.22 and 4.84 hours), with the exception of the highest dose group where the half-life was prolonged on Day 1 (7.06 hours) and Day 21 (6.34 hours) compared to the other dose groups. No relevant accumulation of ESN364 was observed after 21 days of administration of 60 or 180 mg q.d. administration, with mean accumulation ratio (R_{ac}) values of 1.23 and 1.18, respectively. Renal clearance seems to be comparable in the 60 or 180 mg q.d. groups, with mean values of 6.83 and 5.34 mL/min, respectively. When comparing ESN364 exposure after single dosing or at steady-state following multiple dose administration for 10 days (healthy males) and 21 days (healthy women), peak and plasma exposures were significantly lower in males. Time to peak exposure was similar for both genders.

Based on plasma concentrations monitored from the first administration (Day 1) to 24 hours after the last administration (Day 22) (i.e., over the time extent of the menstrual cycle during presence of study drug in the body), the time to reach the peak concentration in LH was lengthened with the 60 and 180 mg q.d. dosages (median time of \approx 17 days) compared to placebo (median time of \approx 8 days). No clear difference between active treatments and placebo could be evidenced in FSH plasma concentrations. The time to reach the peak concentration in total and free estradiol was lengthened with the 60 and

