2.2 SECONDARY OBJECTIVES

Secondary objectives are to evaluate in early postmenopausal women suffering from hot flashes:

- the effect of ESN364 on the severity and frequency of hot flashes, in terms of changes in weekly Hot Flash Score from baseline to Weeks 4 and 8, and at follow-up;
- the effect of ESN364 on the frequency of hot flashes, in terms of changes in weekly Hot Flash Frequency from baseline to Weeks 4, 8, and 12, and at follow-up;
- the effect of 12-week administration of ESN364 on hot flash interference on daily life, in terms of changes from baseline over time in Hot Flash Related Daily Interference Scale (HFRDIS);
- the effect of 12-week administration of ESN364 on climacteric symptoms, in terms of changes from baseline over time in Leeds Sleep Evaluation Questionnaire (LSEQ), Greene Climacteric Scale (GCS), and Sheehan Disability Scale (SDS);
- the PD effect of 12-week administration of ESN364, in terms of changes over time in plasma concentrations of LH, FSH, E2, SHBG, leptin, insulin, C-peptide, and glycated hemoglobin (HbA1c);
- safety and tolerability of 12-week administration of ESN364, in terms of AEs, clinical laboratory tests, plasma bone density marker concentrations (bone alkaline phosphatase [BALP] and carboxy-terminal telopeptide of type I collagen [CTX]), vital signs, ECG, and physical examination.

Exploratory objectives are to:

- evaluate the effect of 12-week administration of ESN364 on body composition (lean mass, fat mass, bone mass/density) assessed by dual-energy X-ray absorptiometry (DEXA);
- assess ESN364 plasma concentrations from sparse PK sampling.

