7. ASSESSMENTS

7.1 TIMING OF ASSESSMENTS

All visits need to be planned in the morning, fasted (for unbiased glucose, insulin, and C-peptide determination). Visit 2 should be planned to allow for first intake of study drugs at the clinical site between 7:00 and 10:00 AM. For each subject, all visits during the treatment period subsequent to Visit 2 should be planned at the same time of the day, in the morning, fasted. A deviation of \pm 1 day is allowed on the visits during the treatment period (Visits 3-5).

At Visits 2 and 5, DEXA will be performed. For practical reasons, the timing of DEXA may vary from the actual time of the visit, depending on the DEXA availability (DEXA appointment):

- The Visit 2 DEXA can be performed prior to Visit 2 during the screening period, as well as at Visit 2 but must be performed before randomization;
- The Visit 5 DEXA can be performed \pm 4 days from the actual time of Visit 5. It is however to be performed before the last dose of the study drug; in case the DEXA appointment related to Visit 5 is scheduled later in time than Visit 5, study drug intake must be continued until DEXA has been performed (study drug intake at home and recorded in the ePRO diary).

An overview of the timing of study drug intake and assessments is given in the [Time and Events Schedule](#).

All assessments will be done predose, except for 3 hours postdose blood sampling for PK and PD assessments at Visit 5 and administration of questionnaires, which can be done at any time during the visit.

7.1.1 *Screening Period (Visit 1)*

Subjects will be given a full explanation of the nature of the study and written informed consent (approved by the local ethics committee) will be obtained according to local requirements before any study-related assessment will be carried out.

Screening (Visit 1) will be performed within 4 weeks prior to the first intake of study drug (with a minimum of 7 days to allow for baseline data collection of Hot Flash Score and Hot Flash Frequency). The visit will consist of screening assessments for eligibility purposes (physical examination, thorough medical history, demographic data, vital signs, ECG, blood/urine samples for PD measurements, clinical laboratory tests, serology, urine drug screen, and urine pregnancy test). In addition, subjects will be trained in the use of the ePRO diary to record their hot flashes severity and frequency, to administer HFRDIS, and to register their study drug intake.

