Collection of hot flashes severity and frequency will be started on an ad hoc basis, but at a minimum twice-daily (morning and evening), via ePRO diary. Data on hot flash severity and frequency collected during the screening period will serve as baseline for Hot Flash Score and Hot Flash Frequency.

An overview of the assessments to be performed at the screening visit is provided in the [Time and Events Schedule](#).

Adverse events and concomitant therapies will be collected from signing of informed consent onwards (screening) through the follow-up visit.

All results from the screening procedure that are needed to evaluate eligibility, including the clinical laboratory results, must be available prior to randomization (Visit 2). Any abnormal assessment at the screening visit will be assessed according to its clinical relevance, and if found relevant, the subject will not be included in the study.

Unscheduled visits may be planned to assess, confirm, and follow-up on an out-of-range clinical laboratory test, vital sign, or ECG value that will determine a subject's eligibility, or in case of a positive urine drug screen. Results of this retest must be available prior to randomization. The result of the retest will be considered for subject eligibility. Findings made during unscheduled visits should be reported in the source documents and in the designated sections of the eCRF.

For screening failures, demographic data, the date of screening and signature of the ICF, and the reason(s) for screening failure will be recorded on the eCRF.

7.1.2 *Treatment Period (Visits 2-5; Weeks 1-12)*

Visit 2 should be scheduled in the morning between 7:00 and 10:00 AM, fasted. In- and exclusion criteria will be reassessed. Eligible subjects will be randomized in a 1:1 ratio to one of the 2 treatment arms (ESN364 90 mg b.i.d. or placebo). Predose assessments for efficacy (questionnaires), PK (ESN364 plasma concentrations), PD (hormone concentrations), and safety (clinical laboratory testing, bone density marker concentrations, vital signs, ECG, and physical examination) parameters will be made to serve as baseline (except for Hot Flash Score and Hot Flash Frequency, for which baseline will be data collected during the screening period).

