Blood samples for clinical laboratory tests will be taken at every visit and should be taken in a fasted state (overnight fast for at least 10 hours) for unbiased glucose, insulin, and C-peptide determination. Physical examination and vital sign assessments will also be made at every visit. An ECG will be recorded at every visit except Visit 4. Levels of the bone density markers BALP and CTX will be assessed at Visits 2 and 5 only.

DEXA will be repeated at Visit 5, before the last dose of the study drug. For practical reasons, the timing of DEXA may vary from the actual time of the visit, depending on the DEXA availability (DEXA appointment). The Visit 5 DEXA can be performed ± 4 days from the actual time of Visit 5. It is however to be performed before the last dose of the study drug; in case the DEXA appointment related to Visit 5 is scheduled later in time than Visit 5, study drug intake must be continued until DEXA has been performed (study drug intake at home and recorded in the ePRO diary).

Adverse events and concomitant therapies will be collected from signing of informed consent onwards (screening) through the follow-up visit.

Compliance towards study drug intake and ePRO completion will be checked at every visit during the treatment period. Compliance towards study drug intake will be assessed by counting returned dosage units in addition to ePRO entries. Any discrepancies between returned dosage units and dosing in the ePRO diary will be discussed with the subject for whom a discrepancy was seen.

An overview of the assessments to be performed during the treatment period is also provided in the [Time and Events Schedule](#).

7.1.3 *Follow-up Period (Visit 6)*

Two to 3 weeks after the last intake of the study drug, subjects will be asked to come to the clinical site for a follow-up visit.

An overview of the assessments to be performed at the follow-up visit is provided in the [Time and Events Schedule](#).

7.1.4 *Unscheduled Visits*

Unscheduled visits can be planned for instance:

- to obtain additional information to ensure safety to the subject. Additional blood and urine samples may be taken at the discretion of the Investigator.

- to collect an additional blood sample for PK assessment if a subject discontinues the study drug due to an AE;

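### Every scheduled on-treatment ECG and vital sign is taken predose, at roughly a quarter to a half of peak ESN364; the Visit 5 recordings could be made at the existing 3-hour postdose point

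*Protocol*

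**What the plan says.** Section 7.1 of the protocol sets one timing rule: "All assessments will be done predose, except for 3 hours postdose blood sampling for PK and PD assessments at Visit 5"; the sentence goes on to except the questionnaires. ECGs and vital signs are not excepted.

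The visits follow from Section 7.1.2 and the Time and Events Schedule. For ECGs: "An ECG will be recorded at every visit except Visit 4". For vital signs: "Physical examination and vital sign assessments will also be made at every visit". At Visit 2 they serve as baseline: "Predose assessments for efficacy (questionnaires), PK (ESN364 plasma concentrations), PD (hormone concentrations), and safety" parameters are collected before the first intake. Visit 6 falls 2-3 weeks after the last intake (Section 7.1.3). Sections 7.5.1.4 and 7.5.1.5 and schedule footnotes o and p give position and rest time but no time relative to dose.

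PK and PD blood is drawn as follows (footnote h): "Predose at Visits 2, 3, and 4; predose and 3 hours postdose at Visit 5". The subject is therefore on site 3 hours after a supervised dose at Visit 5.

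Section 1.3 reports, for women dosed for 21 days, absorption "with median t_{max} of 3.00 to 4.00 hours" and a "mean half-life ranged between 4.22 and 4.84 hours" for the dose groups below 180 mg. At 180 mg q.d. the half-life was 7.06 h on Day 1 and 6.34 h on Day 21.

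Section 2.2 lists among the secondary objectives "safety and tolerability of 12-week administration of ESN364, in terms of AEs, clinical laboratory tests", followed by bone markers, vital signs, ECG and physical examination.

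**The concern.** The study gives 12 weeks of dosing, against at most 21 days in Phase I, and names ECG and vital signs as part of its safety objective. All scheduled on-treatment recordings sit at the low point of the concentration curve. If ESN364 has an effect on QTcF, blood pressure or heart rate that follows plasma concentration, these recordings would tend to understate it, and a clean result would describe predose exposure only.

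The QTcF categories in Section 9.1.5 (>450, >480 and >500 ms; increases >30 and >60 ms) will be filled mainly from these ECGs. The withdrawal criterion in Section 8.2 asks for confirmatory ECGs within 10 minutes of the initial one, so a scheduled predose ECG is confirmed at essentially the same exposure.

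Blood pressure and heart rate deserve a thought as well as QTcF. Section 1.2.3 reports slightly lower blood pressure and slightly higher heart rate in monkeys, and palpitations were reported in Phase I (Sections 1.3 and 1.5).

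**Working it through.** The protocol states no exposure figure for its ECGs or vital signs, so there is nothing to reproduce. The check has two parts: counting the recordings, and estimating the concentration at which they fall.

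**Recordings per subject**

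| Visit | Drug status | ECG | Vital signs |
|---|---|---|---|
| 2 | before first dose | yes | yes |
| 3 (Week 4) | on treatment, predose | yes | yes |
| 4 (Week 8) | on treatment, predose | no | yes |
| 5 (Week 12) | on treatment, predose | yes | yes |
| 6 | 2-3 weeks after last dose | yes | yes |

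With 40 subjects planned on active treatment and no drop-out, that is 40 × 2 = 80 on-treatment ECGs and 40 × 3 = 120 sets of vital signs. None is scheduled postdose.

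**Inputs for exposure**

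- tmax 3 or 4 h, and half-life 4.22, 4.84, 6.34 or 7.06 h (Section 1.3, women).
- Time since the previous dose: nominally 12 h. Section 5.7 prefers evening doses between 7 and 10 PM and morning doses between 7 and 10 AM. The gap can thus run from 9 h (10 PM to 7 AM) to 15 h (7 PM to 10 AM).
- No half-life is given for 90 mg b.i.d., so the full range is carried.

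**(a) Simple decay from the peak:** fraction = 0.5^((t − tmax)/half-life).

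For example, 0.5^((12 − 3)/4.22) = 0.228 and 0.5^((12 − 4)/7.06) = 0.456.

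**(b) One-compartment oral model at steady state**, interval τ = 12 h, with ke = ln 2/half-life and ka solved from ln(ka/ke)/(ka − ke) = tmax. C(t) is proportional to e^(−ke·t)/(1 − e^(−ke·τ)) − e^(−ka·t)/(1 − e^(−ka·τ)). Each value is divided by the modelled peak.

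| Half-life (h) | tmax (h) | (a) 12 h | (b) 12 h | (b) 3 h postdose |
|---|---|---|---|---|
| 4.22 | 3 | 0.228 | 0.297 | 0.995 |
| 4.22 | 4 | 0.269 | 0.404 | 0.997 |
| 4.84 | 3 | 0.276 | 0.334 | 0.994 |
| 4.84 | 4 | 0.318 | 0.429 | 0.998 |
| 6.34 | 3 | 0.374 | 0.415 | 0.991 |
| 6.34 | 4 | 0.417 | 0.489 | 0.999 |
| 7.06 | 3 | 0.413 | 0.448 | 0.991 |
| 7.06 | 4 | 0.456 | 0.515 | 1.000 |

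At 12 h the predose recording is at 23-46% of peak by (a) and 30-52% by (b), which includes carry-over from earlier doses. Over the 9-15 h gap, (a) spans 0.139 (15 h, tmax 3 h, half-life 4.22 h) to 0.612 (9 h, tmax 4 h, half-life 7.06 h). A recording 3 h postdose would be at about 99-100% of modelled peak.

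**The case against.** The case for leaving the schedule alone has real substance.

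- **Nothing is contradicted.** The protocol never says its ECGs or vital signs are meant to capture peak effect. They are summarised descriptively, within one of several secondary objectives of a proof-of-concept study. This stands.
- **The earlier cardiac evidence is reassuring.** Sections 1.2.3 and 1.3 report no significant hERG inhibition, no effect on PR, QRS or QTc in monkeys, and no clinically relevant trend in median ECG or vital-sign values in Phase I, which went up to 180 mg q.d. Section 1.5 adds that vital signs and ECG were normal with the reported palpitations. Under model (b), peak at 90 mg b.i.d. is about 60-70% of peak at 180 mg q.d. This lowers the weight of the point but does not remove it, because the protocol does not say when the Phase I ECGs were taken relative to dose.
- **The QTcF rules are not confined to scheduled visits.** A reader might infer that the withdrawal and stopping rules can never be met near peak. The text does not support that: Section 7.1.4 allows unscheduled safety visits, and a postdose ECG could be taken then. What is true is that none is required.
- **Predose is not drug-free.** A reader might infer that a drug effect would be missed altogether. At a quarter to a half of peak, an effect that persists, or does not track concentration, could still be seen.
- **No QTcF bias is shown.** The percentages are concentration ratios. The protocol gives no exposure-QTcF relation, so they cannot be turned into milliseconds.
- **Moving the Visit 5 recording has a price.** It gives up the Week 12 reading that matches the predose baseline and Visit 3, and shifts the clock time by 3 hours. This stands and is taken up in the fix.

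**Conclusion.** The point holds as a modest design weakness. No scheduled on-treatment ECG or vital sign is taken near peak ESN364: at a nominal 12 h they fall at about 23-46% of peak by decay, or 30-52% by the steady-state model. A concentration-related effect could therefore be understated in the planned tables.

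The figures assume linear kinetics and carry the Phase I tmax and half-lives over to postmenopausal women on 90 mg b.i.d. Section 1.3 notes exposure above dose proportionality at 180 mg, so they are approximate. At the nominal time, every combination of inputs still puts the predose recording at about half of peak or less.

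It would go too far to conclude that a QT effect is being hidden, that the safety rules are inoperative, or that the study can tell Phase IIb nothing about cardiac safety. The documents show a gap in what is measured, not an effect that was missed. The point is worth acting on because the subject is already on site at close to the right time.

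**What to change.** In Section 7.1, the Time and Events Schedule (ECG and vital-sign rows, footnotes o and p) and Sections 7.5.1.4-7.5.1.5:

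- Take the Visit 5 ECG and vital signs 3 hours postdose, just before the existing PK/PD draw, and add them to the exceptions in the timing sentence of Section 7.1.
- Keep the Visit 3 ECG and the Visit 3 and 4 vital signs predose.
- Label the Visit 5 results as near-peak in the QTcF and vital-sign tables, and base their interpretation on active versus placebo at that visit, where both arms share the same time since dose and clock-time shift.

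This needs no extra visit, recording or waiting time, and it pairs a near-peak ECG with a plasma concentration. The cost is the Week 12 trough reading. Change from Week 4 to Week 12 within an arm would also mix treatment duration with time since dose, and placebo does not separate those two. A site that can repeat the recording may keep both the predose and the 3-hour reading.

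If the timing is not changed, state in the protocol and the report that ECG and vital-sign conclusions apply to predose exposure only. No QTcF threshold, withdrawal rule or stopping rule is altered by either option.

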7.2 PHARMACOKINETIC EVALUATIONS

7.2.1 *Blood Sample Collection and Handling*

Venous blood samples will be collected for analysis of ESN364 in plasma according to the time points defined in the [Time and Events Schedule](#). The exact date and time of blood sampling must be recorded in the source documents and on the eCRF.

Blood samples of approximately 2 mL will be collected by venipuncture or indwelling cannula in the forearm into vacuum tubes containing lithium heparin (Venoject green top or equivalent). Immediately after blood collection, the plasma will be separated in a refrigerated centrifuge (4°C) for 10 minutes at ca 1500 g and transferred with a sterile plastic pipette into 2 polypropylene tubes with at least 400 µL of plasma per tube. In case immediate centrifugation is not possible, the samples should be chilled in an ice bath for a maximum of 30 minutes after blood collection until centrifugation.

After appropriate labeling, the plasma samples will be stored below -20°C at the clinical site. Thereafter, the frozen plasma samples will be transported/shipped on dry ice to the central laboratory (BARC, Gent, Belgium), where they will be collected and kept frozen below -20°C until shipment to the bioanalytical laboratory (SGS, Wavre, Belgium).

Further procedures for sample collection, shipment, processing, and storage are described in the laboratory manual.

7.2.2 *Bioanalysis*

Samples for determination of plasma ESN364 concentrations will be analyzed by a qualified vendor (SGS, Wavre, Belgium) under the responsibility of the Sponsor, using a validated analytical method (liquid chromatography with tandem mass spectrometric [LC-MS/MS]).

Samples that remain after protocol-specific assessments have been performed may be used for further exploratory work on PK, metabolites, plasma protein binding, protein analysis, and biochemistry. No human deoxyribonucleic acid (DNA) or ribonucleic acid (RNA) analysis will be performed.

7.2.3 *Pharmacokinetic Endpoints*

Assessment of plasma ESN364 concentrations will be exploratory.

